5.2 Exclusion Criteria

Subjects will not be eligible if they meet any of the following criteria at the Screening and Baseline Visits unless specified otherwise:

- Presence of systemic or localized diseases, conditions, or medications that could interfere
 with assessment of safety and efficacy or that compromise immune function including
 psoriasis
- Subject has been diagnosed with diabetes mellitus
- 3. Subject has a history of keloid formation
- 4. Injectable common wart(s) located in areas with existing dermatologic conditions (such as psoriasis) or with an underlying inflammatory conditions (such as arthritic joints), or tattoos or implants/piercing/hardware or marking that may conceal responses or reactions are excluded from injection.
- Existing/planned pregnancy, childbirth in the past six months prior to the Baseline Visit, or breast feeding, or plan on donating eggs or sperm during the study and in the month following the last injection.
- 6. Treatment of warts with liquid nitrogen, carbon dioxide, electrodessication, laser, surgery, simple occlusion (e.g. duct tape), salicylic or related acids, OTC treatments, cantharidin, or other treatments (other than immunotherapy or those intended to stimulate immune response) within 4 weeks of the Baseline Visit
- 7. Treatment with immunotherapy (DPCP, DNCB or other), imiquimod, 5-fluorouracil, bleomycin, podophyllin or any other wart immunotherapy or treatment designed to stimulate immune response (except for treatments already listed in exclusion criterion 6) within 12 weeks of the Baseline Visit
- 8. Recalcitrant warts defined as those not successfully treated by five or more treatments (excluding OTC treatments).
- Abnormal (low < 5 mm or high >25 mm) baseline result to the Delayed Type Hypersensitivity (DTH) test
- 10. Subject has a condition or treatment resulting in being immunocompromised
- 11. Systemic treatment (such as oral or injected) with cimetidine, zinc supplements at a dose higher than 20 mg of elemental zinc daily or an immunosuppressive drug (such as: azathioprine, 6-mercaptopurine, methotrexate, infliximab, adalimumab, etanercept, systemic steroids, etc.) within 12 weeks of the Baseline Visit. Note that subjects should not discontinue

Nielsen- CFW-2D Page 24 of 54

use of immunosuppressive therapy for the purpose of entering the study as the underlying conditions also could interfere with the study.

- 12. Subject has used any investigational agent within 30 days prior to the Baseline Visit or within 5 half-lives of that investigational agent prior to the Baseline Visit (whichever is longer)
- 13. Previous treatment of warts by intralesional injection with any type of candida extract (including CANDIN)

5.3 Discontinuations

Subjects have the right to withdraw from the study at any time for any reason without penalty. The Investigator also has the right to withdraw subjects from the study if he/she feels it is in the best interest of the subject or if the subject is uncooperative or non-compliant. It is understood by all concerned that an excessive rate of withdrawal can render the study un-interpretable; therefore, unnecessary withdrawal of subjects should be avoided. Should a subject decide to withdraw or if the Investigator decides a subject should be withdrawn, all efforts will be made to complete and report the observations as required in Section 7.6 - Early Termination Visit.

An Early Termination Visit should be completed at the time of the decision to withdraw the subject, or as soon as possible thereafter, and the reason for withdrawal from the study should be documented. If the reason for removal of a subject is an AE or an abnormal laboratory test result, the principal specific event or test will be recorded as the reason for study discontinuation. If this decision is made because of a related SAE, the study drug is to be discontinued and appropriate medical interventions are to be taken. The Investigator will notify the Sponsor immediately. All unresolved, possibly related and related AEs and SAEs will be followed until resolution, or until the Investigator deems the event(s) to be chronic or stable, or until the subject is lost to follow-up.

The criteria for enrollment must be followed explicitly. If a subject who does not meet enrollment criteria is inadvertently enrolled, that subject should be discontinued from the study. If this subject received CANDIN, he/she should come back, if possible within 1 week of the last visit, for safety and efficacy evaluations as required in Section 7.6 - Early Termination Visit.

Reasons for study drug discontinuation include:

- The Investigator decides that the subject should be withdrawn (see above).
- The attending or general physician requests that the subject be withdrawn from the study
- The subject for any reason requires or receives treatment with another therapeutic agent or treatment for their warts. In this case, discontinuation from the study occurs immediately upon introduction of the new agent
- The subject for any reason requires treatment with concomitant medication that is excluded on study.
 In this case, discontinuation from the study occurs immediately upon introduction of the concomitant medication. The Early Termination Visit should occur before the introduction of the concomitant medication if possible.
- The subject is lost to follow-up, in this case, a reasonable attempt to contact the subject and ascertain
 his/her status must be made and these attempts must be documented. The effort will include three or
 more documented attempts then a certified letter requesting the subject contact the site. The

Nielsen- CFW-2D Protocol Final version 5.0: 06Dec2016 Investigator or one of his/her staff members should contact the subject either by telephone, e-mail, or letter to determine as completely as possible the reason for the withdrawal and to schedule the Early Termination Visit. If the subject intends to withdraw from the study, the Early Termination Visit should occur as soon as possible.

- The Sponsor or Regulatory Authorities, for any reason, stops the study. All subjects will be discontinued
 from the study and notified of the reasons for the discontinuation. Subjects may be asked to continue
 with follow-up visits as outlined in Appendix A or to complete the Early Termination Visit.
- The Sponsor, Investigator, or Regulatory Authorities, for any reason, discontinues a site's participation.
 All subjects at that site will be discontinued from the study (unless an alternative, local site is active) and notified of the reasons for the discontinuation. Subjects may be asked to complete the Early Termination Visit and may continue with one or both follow-up visits as outlined in Appendix A.
- Pregnancy at any time during the study. The subject will be followed as outlined in Section 9.4 -Pregnancy Reporting.
- The subject may withdraw from the study for any other reason, including withdrawal of consent. See above.

6 TREATMENT

6.1 Treatment Administered

Subjects who fulfill all the inclusion and none of the exclusion criteria may be accepted in the study. Each subject should read and sign an informed consent form prior to any screening procedures being performed. This study involves a comparison of an intralesional injection of CANDIN with an intralesional injection of placebo (unpreserved normal saline solution) in common warts. Subjects will receive one (Cohorts 1 and 2) or more (Cohort 3) intralesional injections every two weeks (14 +/- 2 days) at the region of the interdigitated base of wart (epidermal/dermal junction) for up to 20 weeks (a maximum of 10 doses per subject) or up to resolution of all injectable warts. Subjects who experience local tolerance issues when dosing is performed at 2-week intervals may be injected at 3-week intervals (21 +/- 2 days) also for a maximum of 10 doses per subject.

Subjects will be included in three cohorts as follows:

- 1. Cohort 1: Approximately 52 subjects will receive 0.3 mL of either CANDIN (n=39) or placebo (n=13) intralesionally in the largest common wart (primary) every second week (14 +/- 2 days) for a maximum of 10 injections. If the primary common wart exhibits a complete response, the second largest injectable common wart of all anatomical regions will be injected with CANDIN at the same dose. If the second largest common wart exhibits a complete response, the third largest of all anatomical regions will be injected. If an injected wart recurs after exhibiting a complete response, it will be re-injected instead of the non-primary injected wart that was injected at the previous visit. This injection strategy will be repeated for a maximum of 10 injections per subject or until all injectable common warts exhibit a complete response, if it occurs before all 10 injections are used.
- 2. **Cohort 2:** Approximately 52 subjects will receive 0.5 mL of either CANDIN (n=39) or placebo (n=13) intralesionally in the largest common wart every second week (14 +/- 2 days) for a maximum of 10 injections. If the primary common wart exhibits a complete

Nielsen- CFW-2D Page 26 of 54 Protocol Final version 5.0: 06Dec2016 response the second largest injectable common wart of all anatomical regions will be injected with CANDIN at the same dose. If the second largest common wart exhibits a complete response the third largest wart of all anatomical regions will be injected. If an injected wart recurs after exhibiting a complete response, it will be re-injected instead of the non-primary injected wart that was injected at the previous visit. This injection strategy will be repeated for a maximum of 10 injections per subject or until all injectable common warts exhibit a complete response, if it occurs before all 10 injections are used.

3. Cohort 3: If the safety data of the 2nd cohort support continuation of the study (defined as medical assessment of the first eight (8) subjects (of cohort 2) completing three (3) injections), the approximately 52 subjects of cohort 3 will receive either 0.3 mL/wart CANDIN (n=39) or placebo (n=13) (total per visit ≤ 1.2 mL). Subjects in cohort 3 must have injectable common warts in at least 2 different anatomic regions. CANDIN or placebo will be injected under the largest wart (primary) per major anatomical region (left or right; arm, hand, leg, foot (excluding sole) or the torso) for a minimum of two (2) and a maximum of four (4) injections per visit every second week (14 +/- 2 days) for a maximum of 10 visits with injections. No more than one wart per anatomical region will be injected on any given visit. If any primary injected wart exhibits a complete response, the next largest injectable common wart will be injected with CANDIN at the same dose (maximum of 4 injections per visit) providing the new injectable wart is not within the same anatomical region as other currently injected warts. If an injected wart recurs after exhibiting a complete response, it will be re-injected instead of the non-primary injected wart that was injected at the previous visit. This injection strategy will be repeated for a maximum total of 10 injection visits per subject or until all injectable common warts exhibit a complete response, if it occurs before the end of the 10 injection visits.

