3.2 Secondary Endpoints

1. Incidence of site injection AE for all subjects and TEAE for subjects randomized to CANDIN

Protocol Final version 5.0: 06Dec2016

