4 STUDY DESIGN

This is a placebo-controlled, double-blind (subject, Investigator, and site staff with the exception of unblinded dedicated staff to handle study medication), phase 2a study with 3 dose cohorts, randomized (concealed) to CANDIN or placebo (3:1). Main study will be up to 20 weeks (10 doses administered every other week) or until a subject has complete resolution of all injected common warts. Subjects who cannot tolerate dosing every 2 weeks due to a local tolerance issue may be injected at 3-week intervals for up to 10 doses, increasing the length of the study to 29 weeks (+/- study windows). Subjects will be followed for 4 months after final injection(s) for evidence of new or reoccurring warts and for safety evaluation.

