5.1 Inclusion Criteria

Subjects may be eligible if they meet all the following inclusion criteria at the Screening and Baseline Visits unless specified otherwise:

- 1. Men or women between the ages of 18 and 65 years inclusively at time of consent
- 2. Subjects presenting with 3 to 20 injectable common warts (verruca vulgaris) for at least 12 weeks at the time of the Baseline Visit
- 3. Subject's common warts for injection must measure between 3 and 20 mm at Baseline Visit and be located on hands, feet (excluding soles), limbs, and/or trunk. Flat, plantar, facial, periungual, genital warts or warts in region of pre-existing inflammatory condition are excluded from injection
- 4. Subjects enrolled into Cohort 3 must have common warts for injection in at least 2 different anatomic regions defined as: left arm, right arm, left hand, right hand, left leg, right leg, left foot (excluding sole), right foot (excluding sole) and torso
- 5. Subject, male or female is willing to use effective contraceptive method for at least 30 days before the Baseline Visit and at least 30 days after the last study drug administration unless not of childbearing potential as defined as post-menopausal for at least 2 years (females) or surgically sterile (tubal ligation, oophorectomy, or hysterectomy for females, and vasectomy for males). The only contraceptive usage exceptions would be individuals in exclusive same sex partnerships and individuals who agree to remain non-sexually active for the duration of the study. Acceptable contraceptive methods for subjects include:
 - Barrier methods such as condom, sponge or diaphragm combined with spermicide in foam, gel or cream;
 - b. Hormonal contraception (oral, intramuscular, implant or transdermal which includes Depo-Provera, Evra and Nuvaring);
 - c. Intrauterine device (IUD)

Female subjects of childbearing potential in a same sex partnership or who are abstinent will still receive pregnancy test as outlined in Appendix A.

6. Mentally and legally capable of giving informed consent prior to any study related procedures

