3.2 Study Procedures and Visit Structure

The study visit schedule and procedures are described in Table 1. The study includes a maximum of approximately 29 weeks of treatment with 1-month (4 weeks) and 4-months (16 weeks) Follow-up visits after the Efficacy Evaluation Visit (V13).

Table 1. Study Procedures and Visit Structure

	Screening Visits		Baseline Visit (Day 1)	Injections Visits ²									Efficacy Evaluation Visit ¹⁰	Follow-up Visits	
Visit	V1 ¹⁴ -30d	V2 ¹	V3 ¹	V4	V5	V6	V7	V8	V9	V10	V11	V12	V13 ¹⁴	V14	V15
Window (days)		±4h ⁵		±2d									±3d	±3d	±7d
Procedure	•													•	
Informed Consent	X														
Inclusion/Exclusion Criteria	X		X												
Demographics	X														
Medical and Surgical History	X		X												
Blood Draw for Safety Labs ¹⁴	X												X		
Urinalysis	X												X		
Pregnancy Test ³	X		X		X		X		X		X		X		
Vital Signs (includes weight and height at screening)	X		X	X	X	X	X	X	X	X	X	X	X		
Physical Examination	X												X		
Full Body Dermatologic Examination to identify the															
presence of any wart type			X				X						X		X
Presence or absence of common warts in designated			37				37						37		37
anatomical areas			X				X						X		X
Evaluation of presence or absence of common warts other			37										37	37	37
than the measured and mapped injectable common warts			X										X	X	X
Common warts measurement and mapping (up to 6															
injectable common warts including all primary injectable			X	X	X	X	X	X	X	X	X	X	X	X	X
warts)															
Evaluation of primary injected wart(s) status				X	X	X	X	X	X	X	X	X	X	X	X
Selection of primary injectable wart(s) ⁹		X													
Selection and Mapping of non-primary common wart(s)			X	v	v	X	X	X	Х	v	Х	X			
for injection ⁸			Λ	X	X	Λ	Λ	Λ	Λ	X	Λ	Λ			
DTH Challenge Injection (30-min observation period)	X^{13}														
DTH Evaluation		X													
Blood Draw for Biomarkers Evaluation	X^6				$X^{6,12}$								X^6		
Randomization			X												
Intralesional Injection (30-min observation period)			X	X	X	X	X	X	X	X	X	X			
Give Subject Diary	X^7		X	X	X	X	X	X	X	X	X	X			
Review/Retrieve Subject Diary		X^7		X	X	X	X	X	X	X	X	X	X		
Medical Photographs ⁴			X		X		X				X		X	X	X
Hypopigmentation and Scarring Assessments ¹¹			X	X	X	X	X	X	X	X	X	X	X	X	X
Concomitant Medications	X	X	X	X	X	X	X	X	X	X	X	X	X	X	X
Adverse Events	X	X	X	X	X	X	X	X	X	X	X	X	X	X	X

- 1. Screening Visit 2 and Baseline Visit may be performed on the same day if all screening information and data are available.

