- 2. If the medical Investigator deems appropriate because of tolerance issues the injection schema may be changed to every 3 weeks instead of 2 weeks for a maximum of 10 doses.
- 3. Female of childbearing potential only. Serum pregnancy at screening and urine pregnancy test at other visits.
- 4. At selected sites, for a maximum of 10 subjects per cohort.
- 5. Post 48h of DTH injection from V1.
- 6. Cohort 1 only.
- 7. DTH Diary
- 8. Applicable only if there is complete resolution of the primary injected wart(s).
- 9. One for Cohort 1 and 2; and up to 4 in Cohort 3.
- 10. If complete resolution of all common warts, not just the primary injected wart(s), is observed at any of the visits following Baseline, the procedures described under Visit 13 will be performed. This visit also will be performed in the event of an early termination.
- 11. To be initially assessed at Visit 3 and prior to the first injection in case of selection and mapping of non-primary common wart(s) for injection (V4 to V12). To be re-assessed at the site of resolved primary and non-primary injected wart(s) must be recorded as an AE if at Baseline (V3), or prior to the first injection in case of selection and mapping of non-primary common wart(s) for injection (V4 to V12) it was assessed as absent.
- 12. Prior to injection.
- 13. On certain occasions, administering the DTH challenge at V1 may result in a difficulty scheduling V2 at the 48 hour time required (for example V1 on a Thursday or Friday resulting in V2 on a weekend). The investigator may perform the DTH challenge on an additional visit after V1 (subvisit) in order to schedule an acceptable V2, provided the DTH challenge is performed within 1 week of V1 and a urine pregnancy test is performed if required for a given subject. Urine pregnancy testing not required for women of non-childbearing potential defined as post-menopausal for at least 2 years or surgically sterile (tubal ligation, oophorectomy, or hysterectomy).
- 14. V1 and V13 should not be scheduled on a weekend if at all possible due to shipping restrictions of blood samples.

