7.3.1 Adverse Events

TEAEs are defined as those occurring during or after the first wart injection of randomized study medication, or existing prior to the time of and worsening after the time of the first study dose, through final Follow-up Visit (V15) or Early Termination/Withdrawal. AEs with onset date prior to the first administration of randomized study medication will be classified as pretreatment AEs.

All AEs are to be coded with Medical Dictionary for Regulatory Activities (MedDRATM) version 17.0.

The frequency (event counts) and incidence (number and percent of subjects) of TEAEs, serious TEAEs, TEAEs leading to withdrawal, TEAEs by severity (most severe grading from

the same preferred terms within the same subjects), and TEAEs by causality (Related versus Not Related), frequent TEAEs (incidence \geq 5% in any treatment groups) will be summarized.

Injection site TEAEs, defined by any preferred terms containing the phrase of "injection site", will be summarized further.

DTH-related AEs that occurred during the DTH Screening time period (e.g., prior to the receiving the randomized study medication) will be summarized separately for DTH Safety population.

All further details collected for AEs will be presented in a listing.

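### Adverse-event tables by arm are not matched for exposure: injections and the length of the AE window depend on wart clearance, and Cohort 3 gets more injections per visit than most of the pooled placebo

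*Protocol*

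**What the plan says.** Protocol 6.1 gives injections every two weeks "for up to 20 weeks (a maximum of 10 doses per subject) or up to resolution of all injectable warts". For Cohorts 1 and 2 the sequence moves from wart to wart up to 10 injections "or until all injectable common warts exhibit a complete response, if it occurs before all 10 injections are used". CANDIN and placebo follow the same rule. Cohort 3 receives 2 to 4 injections per visit, in different anatomical regions. Each cohort has 39 CANDIN and 13 placebo subjects, and SAP 7.1 presents summaries for three CANDIN groups and one pooled placebo group.

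When clearance of all common warts "is observed at any of the visits following Baseline, the procedures described under Visit 13 will be performed" (SAP Table 1, footnote 10). V14 and V15 are described as "with 1-month (4 weeks) and 4-months (16 weeks) Follow-up visits after the Efficacy Evaluation Visit (V13"). SAP 3.1 asks for both visits in subjects who clear early, and Protocol 4 states: "Subjects will be followed for 4 months after final injection(s) for evidence of new or reoccurring warts and for safety evaluation". TEAEs are counted from the first wart injection to V15 or early termination.

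Protocol 3.2 sets the secondary endpoint as "Incidence of site injection AE for all subjects and TEAE for subjects randomized to CANDIN". SAP 7.3.1 summarises "The frequency (event counts) and incidence (number and percent of subjects) of TEAEs, serious TEAEs, TEAEs leading to withdrawal", and Protocol 14.5.2.1 is similar. SAP 6.5 gives a separate frequency table of injections. No AE rate per injection or per unit of time appears in the available text.

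**The concern.** A subject who clears early receives fewer injections and reaches V15 sooner. If CANDIN clears more subjects than placebo, its subjects have on average fewer occasions for an injection-site reaction and fewer weeks in which any AE can be counted. A crude percentage then favours CANDIN even when each injection carries the same risk in both arms.

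A second imbalance comes from pooling placebo. Cohort 3 CANDIN subjects all have several injections per visit, but two thirds of the pooled placebo subjects have one. This makes Cohort 3 CANDIN look worse and Cohorts 1 and 2 look better.

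Safety and tolerability is the only secondary objective visible in the documents. Choosing among the three regimens depends partly on these tables.

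**Working it through.** **Inputs from the documents.** At most 10 doses, 2 weeks apart (3 weeks if poorly tolerated); V15 is 16 weeks after V13; 39 CANDIN and 13 placebo per cohort; 2 to 4 injections per visit in Cohort 3.

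**Assumptions.** V13 falls 2 weeks after the last dose. A share c of an arm clears all injectable warts early, after K injection visits. Each injection carries the same independent AE risk q in both arms. The documents give no value for c, K or q.

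**1. The plan's own durations.** Ten doses have nine intervals. 9 × 2 + 2 = 20 weeks; 9 × 3 + 2 = 29 weeks; 29 + 16 = 45 weeks. All three agree with the protocol synopsis.

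**2. Exposure of an early clearer (2-week schedule).** V15 falls at week 2K + 16, against week 36 for a full course.

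| K | Share of doses | V15 at week | Share of 36 weeks |
|---|---|---|---|
| 4 | 40% | 24 | 67% |
| 6 | 60% | 28 | 78% |
| 8 | 80% | 32 | 89% |

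**3. Base case, one injection per visit.** Take c = 40% on CANDIN and 5% on placebo, K uniform over 2 to 9 (mean 5.5), q = 5%.
- Mean injections: 0.40 × 5.5 + 0.60 × 10 = 8.2 on CANDIN; 0.05 × 5.5 + 0.95 × 10 = 9.8 on placebo.
- Mean weeks to V15: 0.40 × 27 + 0.60 × 36 = 32.4; 0.05 × 27 + 0.95 × 36 = 35.55.
- Chance of at least one injection-site AE: 1 − 0.95^10 = 40.1% for a full course. The average of 1 − 0.95^K over K = 2 to 9 is 24.1%.
- CANDIN: 0.40 × 24.1 + 0.60 × 40.1 = 33.7%. Placebo: 0.05 × 24.1 + 0.95 × 40.1 = 39.3%. The difference is −5.6 points with identical risk per injection.

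**4. Range.** Same formula, CANDIN minus placebo, in percentage points:

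| Clearing, CANDIN v placebo | K | q = 2% | q = 5% | q = 10% |
|---|---|---|---|---|
| 20% v 5% | 2–9 | −1.2 | −2.4 | −3.4 |
| 40% v 5% | 2–9 | −2.8 | −5.6 | −8.0 |
| 50% v 10% | 2–9 | −3.1 | −6.4 | −9.1 |
| 20% v 5% | 6–9 | −0.6 | −1.2 | −1.6 |
| 10% v 2% | 6–9 | −0.3 | −0.7 | −0.9 |

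In the base case with very common reactions, the gap shrinks to 2.1 points at q = 50% and 0.2 at q = 80%, because nearly every subject has a reaction early.

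**5. Cohort 3 against pooled placebo.** Base case with m injections per visit, so K visits give mK injections. Pooled placebo = (26 × 39.3% + 13 × Cohort 3 placebo) / 39.

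| m | Cohort 3 CANDIN | Cohort 3 placebo | Pooled placebo | CANDIN − pooled | CANDIN − own placebo |
|---|---|---|---|---|---|
| 2 | 55.1% | 63.0% | 47.2% | +7.9 | −7.9 |
| 3 | 68.9% | 77.3% | 52.0% | +16.9 | −8.5 |
| 4 | 77.9% | 86.0% | 54.9% | +23.0 | −8.1 |

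Pooling also adds to the understatement in Cohorts 1 and 2. Their 33.7% set against 47.2% to 54.9% is a gap of 13.5 to 21.2 points, of which 5.6 come from early stopping.

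**6. Other AEs.** At a constant weekly rate giving 40% over 36 weeks, the three K = 2–9 scenarios give differences of about 1 to 3 points.

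**The case against.** A reader might infer that AE observation stops at clearance. The documents do not support that: early clearers still have V14 and V15, and TEAEs run to V15. Only two narrower parts end sooner. Diary review ends at V13, and Protocol 9.3 captures SAEs to 30 days after the last wart injection.

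A reader might also infer that the tables flatter CANDIN generally. For Cohort 3 against pooled placebo, step 5 shows the reverse.

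It is tempting to use the planning rates of 70% and 24% as clearance rates. They concern the primary wart(s), whereas injections stop only when all injectable warts clear. Entry requires "Subjects presenting with 3 to 20 injectable common warts (verruca vulgaris"), and Cohorts 1 and 2 treat one wart at a time. Clearance of everything may be late and uncommon, and the effect of early stopping may then be under 2 points. This objection stands and sets the low end of the range.

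Further points also stand in part. Subjects were selected for a DTH response of at least 5 mm, so reactions may be common and early, and subject percentages then move little. With 39 subjects per group, the standard error of the base-case difference is 10.9 points, so 5.6 points is about half of one. No between-arm safety test is visible, and the TEAE part of the protocol's secondary endpoint names only CANDIN subjects. Events per injection could be derived by dividing tabulated event counts by injection counts, but incidence over a common early exposure could not. Finally, crude incidence over the course as given validly describes the regimen, so it should stay.

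**Conclusion.** The point holds in a limited form. Exposure to injections and the length of the AE window follow from response, and injections per visit differ between Cohort 3 and most of the pooled placebo. The crude tables allow for neither. From early stopping alone, the understatement for CANDIN in Cohorts 1 and 2 is about 0.3 to 9 points, for clearance of 10 to 50% against 2 to 10% and a risk of 2 to 10% per injection. For Cohort 3 against pooled placebo, the overstatement is about 8 to 23 points at 5% per injection under base-case clearance. All of these rates are assumptions.

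The direction thus differs by cohort, and the pooling effect can be the larger of the two. This is a cheap improvement to the safety reporting of a phase 2a trial. It does not invalidate the planned tables, and the documents give no ground for making exposure-adjusted rates the sole basis of the tolerability conclusion.

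**What to change.** Keep the crude counts and percentages. Add to SAP 7.3.1, by treatment group, and refer to it from Protocol 14.5.2.1:

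- (a) Injection-site TEAEs per injection given, and the percentage of subjects with at least one over a common early exposure, such as the first few injection visits. Show Cohort 3 also against its own 13 placebo subjects or per injection.
- (b) Other TEAEs per subject-week from V3 to the last visit.

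Report these beside the crude figures when interpreting CANDIN against placebo.

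The sponsor should also reconcile the passages that fix the window. Injections end on clearance of all injectable warts (Protocol 6.1), which SAP 6.1 defines as measured warts, but the early V13 is triggered by clearance of all common warts (SAP Table 1, footnote 10).

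The cost is SAP wording and one or two tables; injection counts and visit dates are already collected. The rates assume roughly constant risk per injection or week. If reactions cluster at the first injections, a per-injection rate will look too high in the arm that stops earlier, which is why the early-exposure percentage and the crude figures belong beside it. Comparison with 13 placebo subjects will be imprecise.
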